## **8.5.2 ECG based endpoints**

### **8.5.2.1 Successful reperfusion 30 minutes after angiogram/PCI**

Successful reperfusion will be analysed using a relative risk for treatment effect as described in Section 8.5.1.

### **8.5.2.2 Sum ST-segment deviation resolution 30-min post-angiogram/PCI**

The sum ST-segment deviation resolution will be described per treatment group by median and quartiles. The Wilcoxon rank sum test test will be performed to test for differences between the two treatment groups.

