2.2 EFFICACY ENDPOINT

The trial is of exploratory nature with the aim to examine the potential benefits of this pharmacoinvasive strategy. Therefore, no confirmatory statistical hypothesis is pre-specified. All statistical tests are of exploratory nature based on descriptive p-values with accompanying 95% confidence limits for formal statistical hypotheses generation. Efficacy for early reperfusion will be evaluated by the number of patients achieving $\geq 50\%$ ST-segment resolution before and after PCI in lead with maximal ST elevation at baseline; % rescue PCI; TIMI flow grades.

An intent-to-treat analysis of all randomised patients will be carried out. After 50 % of the planned recruitment a formal interim analysis will be performed by the DSMB to evaluate and advise the Executive Committee on the feasibility and justification of enlarging the sample size with provision to proceed with a confirmatory trial.

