5.1.2. Clinical events

Death, shock, heart failure, recurrent MI, rescue PCI and aborted MI will be recorded and assessed as single or composite endpoints for evaluation as noted in the statistical analytical plan. All statistical tests on clinical events are of exploratory nature based on descriptive p-values with estimation of 95% confidence limits for formal statistical hypotheses generation.

For definitions of clinical events: see APPENDICES

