## 7 Interim analysis

At the interim analysis when about 300 patients were randomized, it was decided the study would continue as planned and the study remains of exploratory nature based on descriptive p-values with estimation of 95% confidence limits for formal statistical hypotheses generation.

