### **8.5.3.2 Need for rescue PCI/revascularization in Group A**

The number of patients who needed rescue PCI/revascularization and the corresponding percentage will be reported. Both the investigator and adjudicated data will be reported.

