## **8.5.4 Angiographic endpoints**

### **8.5.4.1 TIMI flow at first coronary angiography**

The number of patients with TIMI flow 0 or 1, 2 and 3 will be reported and percentage will be calculated on those for which a TIMI flow measurement was available. The comparison between the treatment groups will be performed by the Cochran–Armitage test for trend.

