## **8.9 Other Endpoints**

### **8.9.1 Within 30-days**

Duration of index hospitalization will be compared between treatment groups by means of a t-test or Wilcoxon rank test, whichever is appropriate. The duration in each treatment group will be described using means and standard deviations, or median and interquartile range, whichever is appropriate.

The mean difference or Hodges-Lehman estimator with a 95% confidence interval will be reported, whichever is appropriate..

Patient still in hospital at day 30 will be analysed as 30 days. The proportion of patients still in hospital at 30 days will be reported.

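### TIMI flow and sum ST-segment deviation resolution get no effect estimate or 95% CI, and the FAS rescue PCI rate gets no CI, although both documents say exploratory results carry 95% limits

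*SAP*

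**What the plan says.** **The commitment.** Protocol 2.2 states: "All statistical tests are of exploratory nature based on descriptive p-values with accompanying 95% confidence limits for formal statistical hypotheses generation". The sentence after it lists the measures of early reperfusion: ST resolution of at least 50% "in lead with maximal ST elevation at baseline; % rescue PCI; TIMI flow grades". Protocol 5.1.2 counts rescue PCI among the clinical events ("Death, shock, heart failure, recurrent MI, rescue PCI and aborted MI will be recorded and assessed as single or composite endpoints") and again promises 95% limits for tests on such events. Protocol 7.5 and SAP 3 add that efficacy and safety events will be reported with 95% limits. SAP 7 confirms after the interim analysis that "the study remains of exploratory nature based on descriptive p-values with estimation of 95% confidence limits for formal statistical hypotheses generation".

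**The FAS analyses in the SAP.**
- Sum ST-segment deviation resolution (8.5.2.2): median and quartiles per arm, then "The Wilcoxon rank sum test test will be performed to test for differences between the two treatment groups". Table 10.1.1 marks its relative-risk cell as not applicable and offers nothing in its place.
- TIMI flow at first and last angiography (8.5.4): counts per category, where "percentage will be calculated on those for which a TIMI flow measurement was available", and a Cochran-Armitage trend test. Table 10.1.3 has a p-value column but none for an estimate or interval.
- Rescue PCI, Group A only (8.5.3.2): "The number of patients who needed rescue PCI/revascularization and the corresponding percentage will be reported".

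**The pooled elderly sets.** The rescue rate gets a 95% CI (9.1.3.2). TIMI flow gets a van Elteren test with combined counts and percentages (9.1.4).

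**Where intervals are planned.** The composite gets a relative risk and a risk difference, each with a 95% CI (8.5.1). Successful reperfusion (8.5.2.1) and aborted infarction (8.5.3.1) follow that method. For length of stay (8.9.1), "The mean difference or Hodges-Lehman estimator with a 95% confidence interval will be reported".

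**The concern.** The trial has no primary hypothesis, margin or power calculation. It asks whether the pharmaco-invasive strategy matches primary PCI in effect and safety, which is a question of estimation. A trend or rank p-value gives neither the size of a difference nor the range of differences still compatible with the data, so a non-significant one is easily read as similarity. For clinical events the protocol guards against this: the last part of Appendix B says that, absent a significant difference, the interval will be used to see how much worse an outcome can be ruled out. TIMI flow and sum ST resolution have no interval to use in that way.

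The pooled analysis raises the same issue. Protocol 7.5 gives a more reliable estimate in the elderly as the reason for combining angiographic data with STREAM-1. For TIMI flow, SAP 9.1.4 yields a stratified test and crude combined percentages, but no study-stratified estimate.

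The pattern looks like an oversight. Length of stay gets a Hodges-Lehmann interval while an endpoint of primary interest analysed by ranks does not, and the rescue rate has an interval in the pooled sets but not in the FAS.

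**Working it through.** The documents state no precision for these endpoints, so there is no figure of theirs to reproduce. The check has two parts.

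**1. Plan against commitment**

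| Endpoint (FAS) | Named in Protocol 2.2? | Between-group? | Planned output | 95% CI? |
|---|---|---|---|---|
| ST resolution ≥50%, worst lead | Yes | Yes | Relative risk, risk difference | Yes |
| TIMI flow, first and last | Yes | Yes | Counts, trend p | No |
| Rescue PCI | Yes | No, Group A only | n, % | No |
| Sum ST-deviation resolution | No; reached by the general wording on all tests | Yes | Median, quartiles, Wilcoxon p | No |

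**2. What the missing intervals would show**

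Inputs: 400 and 200 patients (Protocol 7.5); expected rescue rate 25-30% (Protocol 5.3.3). TIMI 3 rates and the SD of sum ST resolution are not in the documents, so both are assumptions shown over a range. No missing data are assumed.

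*Rescue proportion, n = 400.* Simple half-width 1.96 × √(p(1−p)/400):
- p = 0.25: 1.96 × √(0.1875/400) = 4.2 points; Wilson interval 21.0% to 29.5%.
- p = 0.30: 1.96 × √(0.21/400) = 4.5 points; Wilson interval 25.7% to 34.7%.

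*TIMI 3 risk difference, common rate p in both arms.* Half-width 1.96 × √(p(1−p) × (1/400 + 1/200)), with √(1/400 + 1/200) = √0.0075 = 0.0866:
- p = 0.50: 1.96 × 0.500 × 0.0866 = 8.5 points
- p = 0.60: 1.96 × 0.490 × 0.0866 = 8.3 points
- p = 0.80: 1.96 × 0.400 × 0.0866 = 6.8 points
- p = 0.90: 1.96 × 0.300 × 0.0866 = 5.1 points

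If the arms differ, 8.5 points remains the maximum, because p(1−p) peaks at 0.5 in each arm.

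*Sum ST resolution, Hodges-Lehmann shift.* Under normality the half-width is 1.96 × SD × 0.0866 × √(π/3) = 0.174 SD. A simulation at 400 v 200 gave 0.173 SD. For an assumed SD of 20, 30 or 40 points this is ±3.5, ±5.2 or ±6.9 points.

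**The case against.** The strongest reply is that little is really lost, and most of it is correct.

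- **The ST measure that the protocol names does get its interval.** At least 50% resolution in the worst lead is analysed by the 8.5.1 method. A reader might infer that the protocol specifically promised limits for sum ST resolution. It does not mention that endpoint, and only the general wording of Protocol 2.2 and SAP 7 covers it.
- **Rescue PCI has no comparator.** A reader might infer that a between-group difference goes unquantified, but none exists. What is missing is the precision of one rate, which anyone can compute from the n/N in Table 10.1.2. No test is run either, so the sentence on tests reaches it weakly; the promise in Protocol 7.5 and SAP 3 for events fits better.
- **A TIMI 3 difference can be derived from Table 10.1.3,** which prints n/N by grade and arm. Only the sum-ST shift cannot be recovered from the planned tables.
- **Imputation.** SAP 5 would impute TIMI flow if more than 1% were missing, while 8.5.4.1 bases percentages on available measurements. A reader might infer that a trend test can never be combined over imputations. That goes too far: the statistic is a linear contrast over its standard error, and 8.5.4.1 does not say how the test treats missing values. Sum ST resolution is exempt from imputation.

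These points narrow the concern but do not remove it. That readers could calculate an interval themselves is no reason to leave it out when the plan says it will be given.

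**Conclusion.** The point holds as a limited reporting gap. Two between-group endpoints of primary interest, TIMI flow and sum ST-segment deviation resolution, have no planned effect estimate or 95% CI, and the FAS rescue rate has no CI. This departs from the general statement in Protocol 2.2 and SAP 7 and is uneven within the SAP itself.

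The documents do not support the wider inference that the trial cannot say which differences it excludes. Its composite, main ECG endpoint and aborted infarction all have intervals. No sample size, power or error rate is affected.

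The precision going unreported is about ±4.2 to 4.5 points for rescue at the protocol's expected rate, about ±5 to 8.5 points for a TIMI 3 difference, and about ±0.17 SD for the sum-ST shift. The last two rest on assumed rates (50-90%, equal in both arms) and an assumed SD; all three rest on full recruitment at 400 v 200 without missing data. Limits of that width matter to a claim of similar reperfusion, so the change is worth making.

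**What to change.** - **SAP 8.5.2.2:** add the Hodges-Lehmann shift with 95% CI, the estimator already used in 8.9.1, beside the Wilcoxon test.
- **SAP 8.5.4:** for first and last angiography, add the risk difference and relative risk for TIMI 3 with 95% CI by the 8.5.1 method. Keep the trend test for the p-value. This also supplies an estimate that can be combined directly if TIMI flow is imputed under SAP 5.
- **SAP 9.1.4:** add the study-stratified TIMI 3 estimate with 95% CI by the 9.1.1 method, beside the van Elteren test.
- **SAP 8.5.3.2:** add a 95% CI, for example Wilson, for the investigator-determined and the adjudicated rescue proportions.
- **Mock tables:** add the columns to Tables 10.1.1 to 10.1.3 and 25.1. Table 24.1 also needs a place for the interval that 9.1.3.2 already promises.

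The cost is a few sentences, some table columns and a little programming. No new data are needed, and the existing tests stay as they are.

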5.1.1 ECGs to be taken/analysed

Twelve-lead ECGs at screening/baseline for initial diagnosis in all patients and subsequently:

- In PhI group:

- 90 min (or earlier if clinically indicated) after bolus tenecteplase
- Immediately before and 30 minutes after the catheterization procedure (with or without PCI/stenting).
- In case of rescue/urgent PCI, ECGs will be taken immediately before the procedure and 30 minutes after the end of the procedure.
- In PPCI group: an ECG will be taken before PCI procedure and 30 min after the PCI procedure.

In all patients, additional ECGs will be recorded before hospital discharge or on day 4, whichever occurs first. Serial ECGs should be taken in case of symptoms of recurrent ischaemia or reinfarction (see tables 4 and 5). ECGs will be centrally adjudicated.

ECG changes will be used to determine:

- Infarct size: It will be calculated at hospital discharge or day 4 whichever is earlier) using Selvester QRS scoring system⁴⁹ previously used in the ASSENT-3/3 Plus and ASSENT-4 PCI studies.^{23, 42}

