7.5 DETERMINATION OF SAMPLE SIZE

As mentioned before this is a hypothesis generating trial. No primary hypothesis or primary endpoint have been formulated. Approximately 600 patients are planned to be randomized with 400 receiving PhI therapy and 200 PPCI. A minimum of approximately 100 patients \geq 70 years of age will be randomized to the PhI arm. The aim is to combine ECG and angiographic data from the latter group with similar data from STREAM-1^{16, 18} in order to have a more reliable estimate of the efficacy of the PhI strategy in elderly patients. The analysis of ECG data, angiographic data and clinical events will be described in detail in the statistical analysis plan. Although the study of 600 patients is not powered to show a difference in clinical events, given the elderly nature of the population there will be ample efficacy and safety events to observe. They will be reported along with their 95% confidence limits. For reference, in patients \geq 60 years from STREAM-1 the 30 day composite of death, shock, heart failure and re-MI ranged between 18 and 20 % for PhI and PPCI groups. Bleeding data in this age group were 1.7 % and 0 % ICH and 8.8 % and 7 % non-intracranial major bleeding respectively. If the study would turn into a confirmatory trial after the interim analysis a primary hypothesis on a combined clinical endpoint will be pre-specified.

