## **6 Endpoints**

### ***6.1 Efficacy endpoints of primary interest***

#### **6.1.1 Clinical endpoint**

The efficacy endpoint of primary interest is all cause death, shock ,CHF and reinfarction at day 30.

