#### **6.1.2 ECG-based endpoints**

- Successful reperfusion: (Worse-lead ST-segment elevation resolution  $\geq 50\%$  30-min post-angiogram/PCI)
- Sum ST-segment deviation resolution 30-min post-angiogram/PCI

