**Table 9.2 Other In-PCI-Hospital Data (PPS)**

**Table 10.1 Endpoints of primary interest (FAS)**

**Table 10.1.1 Clinical and ECG based endpoints (FAS)**

	PhI (N=#)	P-PCI (N=#)	Relative Risk	P-value	PhI Better	P-PCI Better
All cause death or shock or CHF or reinfarction within 30 days	n/N (%)	n/N (%)	#	#		
Successful reperfusion* 30 minutes Post-angiogram/PCI	n/N (%)	n/N (%)	#	#		
Sum ST-segment deviation resolution (%) 30 minutes Post-angiogram/PCI	Median (Q1; Q3)	Median (Q1; Q3)	NA	#		
Aborted myocardial infarction	n/N (%)	n/N (%)	#	#		

\*: Worst-lead ST-segment elevation resolution  $\geq 50\%$

NA: not applicable

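### Percent sum ST-segment deviation resolution is compared by a valid but unadjusted Wilcoxon test; a rank analysis of covariance on the baseline sum would cost almost nothing and may gain some precision

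*SAP*

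**What the plan says.** SAP 6.1.2 lists "Sum ST-segment deviation resolution 30-min post-angiogram/PCI" under the heading "Efficacy endpoints of primary interest". The analysis is in SAP 8.5.2.2: "The sum ST-segment deviation resolution will be described per treatment group by median and quartiles", followed by "The Wilcoxon rank sum test test will be performed to test for differences between the two treatment groups". No covariate or stratification is named, and no between-arm estimate or interval is planned. Mock Table 10.1.1 shows the row as "Sum ST-segment deviation resolution (%) 30 minutes Post-angiogram/PCI" and marks the effect measure as not applicable.

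On baseline, Protocol 5.1.1 plans "Twelve-lead ECGs at screening/baseline for initial diagnosis in all patients and subsequently" at set later times. Randomisation is stratified by centre only (Protocol 7.4). SAP 5 excludes this endpoint from multiple imputation, so the analysis uses observed values.

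On status, Protocol 7.5 states that there is no primary hypothesis or primary endpoint, and SAP 7 confirms that the trial stayed exploratory after the interim analysis. Both Protocol 2.2 and SAP 7 promise 95% confidence limits alongside descriptive p-values.

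**The concern.** The endpoint is a percentage of a baseline value, so every patient who has a result must also have a baseline sum ST deviation. The analysis uses that value only as a denominator.

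Dividing by baseline removes its influence only if residual ST deviation is proportional to baseline. If residual deviation rises less than proportionally (a log-log slope below 1), patients who start with more deviation show a larger percent resolution. That spread has nothing to do with treatment, yet it stays in the ranks that the Wilcoxon test compares. A chance difference between the arms in initial deviation would also carry over, to the extent of the remaining relation. Entry requires a combined elevation of at least 4 mm with no upper limit (Protocol 3.3.1), so initial deviation can vary widely.

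At stake is some precision on the one continuous ECG comparison between arms that the SAP places among its endpoints of primary interest.

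**Working it through.** **Inputs from the documents.** Sample size: "Approximately 600 patients are planned to be randomized with 400 receiving PhI therapy and 200 PPCI". The plan states no power, effect, SD or correlation for this endpoint, so there is no figure to reproduce.

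**Assumed inputs.** Two-sided 5% level; ρ, the correlation of percent resolution with baseline sum ST deviation, from 0 to 0.5; and an effect chosen so that the unadjusted Wilcoxon test has 80% power. The 80% is only an anchor for the illustration.

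**Formula.** Under normality the Wilcoxon test has efficiency 3/π relative to the t-test, and adjustment multiplies the variance by 1 − ρ². With SE = √(1/400 + 1/200) = 0.0866:

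- Power = Φ( d·√(3/π) / (SE·√(1 − ρ²)) − 1.96 )
- For 80% at ρ = 0: d·√(3/π) = (1.96 + 0.8416) × 0.0866 = 0.2426, so d = 0.248 SD.
- At ρ = 0.3: 0.2426 / (0.0866 × 0.954) − 1.96 = 0.977, and Φ = 83.6%.

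| Assumed ρ | Variance factor | Gain over unadjusted (points) | Adjusted N matching 600 unadjusted |
|---|---|---|---|
| 0 | 1.00 | 0 | 600 |
| 0.1 | 0.99 | 0.4 | 594 |
| 0.2 | 0.96 | 1.6 | 576 |
| 0.3 | 0.91 | 3.6 | 546 |
| 0.4 | 0.84 | 6.4 | 504 |
| 0.5 | 0.75 | 9.9 | 450 |

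**Simulation, normal data** (400 v 200, 3,000 runs per setting). Wilcoxon against regression of outcome ranks on arm and baseline ranks, a close relative of Quade's test: 79.1 v 79.2% at ρ = 0, 81.2 v 82.5% at 0.2, 79.7 v 82.5% at 0.3, and 79.1 v 88.3% at 0.5. Over ρ from 0 to 0.7, null rejection was 4.3 to 5.9% for the Wilcoxon test and 4.3 to 5.8% for the rank analysis of covariance. Both hold their level.

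**Simulation, percent resolution built from skewed sums** (1,500 runs; assumed baseline median 12 mm, log SD 0.5, residual log SD 0.6 or 0.8; effect fixed relative to the residual SD):

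| Log slope | Spearman with baseline | Wilcoxon v rank ANCOVA (%) |
|---|---|---|
| 1.0 | 0.00 | 81.5 v 81.3; 82.1 v 81.7 |
| 0.8 | 0.16; 0.12 | 81.7 v 82.5; 79.4 v 80.4 |
| 0.6 | 0.30; 0.23 | 74.1 v 77.9; 77.6 v 79.3 |
| 0.4 | 0.43; 0.34 | 69.8 v 79.3; 73.9 v 79.5 |

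The simulation error of each power is about 1 point (√(0.8 × 0.2/1,500) = 0.010), so the differences at slope 1 are not evidence of a loss. Quade's test itself, run in the same kind of model, gave 80 v 80% at slope 1 and 77 v 80% at slope 0.5 with residual SD 0.8. In that second setting the correlation is 0.25/√(0.25² + 0.8²) = 0.30.

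**Form of adjustment.** Linear ANCOVA on the raw skewed percentage did worse than the planned test where there was no relation with baseline (71 v 82% with residual SD 0.8). The adjustment should therefore be rank-based.

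**Chance imbalance.** A 1.96-SE imbalance in baseline is 1.96 × 0.0866 = 0.170 baseline SD. It shifts the outcome by ρ × 0.170: 0.034 SD at ρ = 0.2, 0.051 at 0.3 and 0.085 at 0.5, against the assumed effect of 0.248 SD.

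**The case against.** The case for leaving the section alone is substantial. Percent resolution already uses baseline, so only a departure from proportionality is left, and that may be small. The documents supply nothing from which to size it. N was not derived from this endpoint, no decision rule depends on its p-value, and the other between-arm comparisons in SAP 8.5 are also unadjusted. The protocol's own ST measure is the number of patients with at least 50% resolution in a single lead (Protocol 2.2), so sum ST deviation is one SAP endpoint among several. All of this stands, and it limits the weight of the point.

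It does not remove the point. Here the covariate is the endpoint's own denominator, so adjusting needs no new data, and a trial of fixed size that generates hypotheses still benefits from precision. SAP 8.11 plans subgroup tests for the ECG endpoints, but none by baseline ST deviation. The SAP also goes beyond a plain rank test elsewhere: 9.1.4.1 stratifies the TIMI flow comparison by study.

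Three stronger readings are tempting and unsupported:

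- **That the Wilcoxon result would be invalid or biased.** Randomisation protects it, and its level holds in simulation.
- **That adjustment would lift the trial's power from 80% to 90%.** The plan states no power, and that figure needs an assumed correlation of 0.5. A gain of 16 points, seen at slope 0.3 with residual SD 0.5, needs a correlation of 0.35/√(0.35² + 0.5²) = 0.57. No section supports either value.
- **That a baseline imbalance would pass in full into the result.** The ratio removes the proportional part, and only the fraction ρ of the rest carries over.

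**Conclusion.** The point holds as a low-cost refinement. The planned test is valid but leaves unused whatever relation remains between percent resolution and baseline. Under the assumptions above, adjustment gains nothing at correlation 0, about 2 points or less up to 0.2, about 3 to 4 at 0.3, and about 6 to 10 at 0.4 to 0.5. There is no loss if the relation is absent.

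The documents cannot say where in that range the trial lies, and the low end is plausible because the endpoint already divides by baseline. That every analysed patient has a baseline sum is inferred from the percent scale and the planned baseline ECG, since neither document defines the sum. Separately, a test alone does not deliver the 95% confidence limits that the plan promises.

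**What to change.** In SAP 8.5.2.2:

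- Make the between-arm test a rank analysis of covariance (Quade): rank percent resolution and baseline sum ST deviation over all analysed patients, regress the first set of ranks on the second, and compare the residuals between arms.
- Use baseline sum ST deviation as the only covariate. Infarct location would add an analyst's choice, because SAP 5 codes it in two categories and SAP 8.11 in three.
- Keep the medians, quartiles and unadjusted Wilcoxon p-value as supporting results.
- Report the Hodges-Lehmann difference with 95% CI, which SAP 8.9.1 already uses for length of stay, and replace the not-applicable entry in Table 10.1.1. State that this interval is unadjusted, so it may differ at the margin from the adjusted p-value.
- Date the change before outcome data are seen. If they have been seen, keep the Wilcoxon test as planned and label the adjusted test a sensitivity analysis.

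The cost is a few sentences in the SAP, one table cell and a few lines of code, on ECG data that the endpoint already requires.
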